8. Be willing to not increase pain medications from baseline through the 3-Month Visit
9. Be willing and able to comply with study-related requirements, procedures, and visits

B.3.3. Exclusion Criteria

In order to participate in the study, a subject must *NOT* MEET ANY of the following exclusion criteria:

1. Had a previous spinal surgery (e.g., lumbar fusion, discectomy, laminectomy, laminotomy)
2. Has a medical, anatomical, and/or psychosocial condition that is contraindicated for commercially available Intellis™ SCS systems as determined by the Investigator
3. Has a diagnosed back condition with inflammatory causes of back pain (e.g., onset of severe pain with activity), serious spinal pathology and/or neurological disorders as determined by the Investigator
4. Be concurrently participating in another clinical study
5. Has an existing active implanted device such as a pacemaker, another SCS unit, peripheral nerve stimulator, and/or drug delivery pump, etc.
6. Has pain in other area(s) and/or medical condition requiring the regular use of significant pain medications that could interfere with accurate pain reporting, study procedures, and/or confound evaluation of study endpoints, as determined by the Investigator
7. Has mechanical spine instability as determined by the Investigator
8. Has undergone, within 30 days prior to enrollment, an interventional procedure and/or surgery to treat back and/or leg pain, which is providing significant pain relief
9. Has unresolved major issues of secondary gain (e.g., social, financial, legal), as determined by the investigator
10. Be involved in an injury claim under current litigation or has a pending or approved worker's compensation claim
11. Be pregnant (determined by urine testing unless female subject is surgically sterile or post-menopausal. If female, sexually active, and childbearing age, subject must be willing to use a reliable form of birth control.)

B.4. Treatment Groups

Subjects meeting the study entrance criteria will be randomized to one of two study treatment groups in a 1:1 ratio:

- Control Treatment Group: Conventional SCS programming approach
 - Stimulation parameters in the 40-250 Hz frequency range will be trialed according to standard practice as described in the Intellis™ labeling/manuals
 - If frequency parameter above 250 Hz is used during the study, the subject will be counted as failure towards Conventional SCS programming approach but will continue to permanent implant.

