- Test Treatment Group: DTM-SCS programming approach
 - As with Conventional SCS programming, stimulation parameters will be trialed according to standard practice as described in the Intellis™ labeling/manuals. Subjects will be given multiple program groups to try. Each DTM-SCS program group will have multiple parameters. The stimulation parameters will be within the specifications described in the Intellis™ labeling/manuals. Each DTM-SCS program group has at least two programs with different pulse rate in the 50 to 1,000 Hz range and each having a maximum pulse width of 1 ms. The subject will progress through each of the program groups until satisfactory pain relief has been reached. The subject will be able to adjust the amplitude of the signals as deemed needed to obtain pain relief. If sufficient pain relief is not achieved with the initial program group, the subject will be instructed to trial another DTM-SCS program group.

B.5. Study Design

B.5.1. Overall Design

This is a post market, open-label, multi-center, prospective, randomized, controlled study to evaluate DTM-SCS in subjects with chronic, intractable pain of the lower back. Data at follow-up visits will be compared between the two treatment groups, and in reference to baseline assessments collected at the beginning of the study.

B.5.2. Bias Minimization

This Investigational Plan and its associated documentation have been designed to minimize potential sources of bias. Each Investigator's qualification for meeting the requirements of this investigational plan will be reviewed prior to their participation in this investigation. Randomization of subjects to one of the two treatment groups will occur after the subject completes Baseline assessments in order to minimize selection bias.

Each therapy, DTM-SCS programs and Conventional SCS programs, will be programmed by clinical representatives of SGX and Medtronic respectively, and in accordance with their Conventional therapy algorithms for optimal pain relief. This will minimize bias related to potential preference by a given clinical representative to a particular SCS therapy.

B.5.3. Comparison Groups

Both groups in the study are active treatment groups. Treatment outcomes from subjects in the DTM-SCS group will be compared to those of the Conventional SCS group.

B.5.4. Blinding

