Subjects will visit the study site where they will be assessed for pain, extent of disability, quality of life, Patient Global Impression of Change, and subject satisfaction. Paresthesia generated by the stimulator will be assessed. Programming adjustments may be made, as needed. Anterior-posterior (AP) and lateral X-ray imaging may be done if significant lead migration is suspected. Subjects will also be assessed for possible adverse events and medication usage.

After the 6 month assessment is completed, subjects in both arms will have an option to change to the other arm if the subject is not receiving sufficient pain relief and desires to try the other arm's parameters. The subject can crossover immediately after completing the 6 month assessment or within 30 days after completing the 6 month assessment. At the time of crossover, imaging may be required to confirm lead location before programming. If the subject has gross lead migration and is not a candidate for a lead revision, the subject may have to be withdrawn due to the inability to program effectively. If withdrawn, the subject would be continued to be followed by their pain physician as a non-study, commercial patient.

B.6.15. 9 Months After Device Activation (\pm 31 days)

Subjects will visit the study site where they will be assessed for pain, extent of disability, quality of life, Patient Global Impression of Change, and subject satisfaction. Paresthesia generated by the stimulator will be assessed. Programming adjustments may be made, as needed. Subjects will also be assessed for possible adverse events and medication usage.

B.6.16. 12 Months After Device Activation (\pm 45 days)

The follow-up visit 12 Months after Device activation is the final scheduled study visit. Subjects will visit the study site where they will be assessed for pain, extent of disability, quality of life, Patient Global Impression of Change, and subject satisfaction. Paresthesia generated by the stimulator will be assessed. Programming adjustments may be made, as

needed. Subjects will also be assessed for possible adverse events and medication usage.

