- Acetaminophen, NSAIDs or other pain medications (new prescriptions or greater than Baseline doses) may only be taken for an acute condition and for a limited duration. For each type of pain medication, dosing should not exceed the maximum daily dosage recommended by the manufacturer and usage should not continue beyond 5 days. Should acute pain medication usage coincide with a follow-up visit, the visit will be postponed until two weeks after acute pain medication usage has been stopped.
- Following trial and permanent implants, the clinical site's standard practice for prophylactic pre-surgery antibiotics and post-surgery pain medications will be followed. Investigators will instruct subjects not to change usage of any other concomitant pain medications.

B.6.18. Device Explant

At any time during the study, a subject may elect to withdraw from the study and have the SCS device system explanted. Additionally, an Investigator may elect to explant a device due to an adverse event.

The Investigator must follow the appropriate guidelines set forth by the Medtronic for returning the explanted device and/or lead(s) as well as the accessories (charger, patient remote control).

B.6.19. Early Subject Withdrawal

Although efforts will be made by Investigators and study staff to encourage subjects to remain enrolled in the study, subjects may withdraw early from the study for a number of reasons, including but not limited to:

- Failure of SCS Trial Phase
- Subject request
- Investigator request
- Subject lost to follow-up
- Subject's death
- Adverse events (e.g., intolerable adverse event occurrence that forces subject to stop participation in the study)

If a subject is considering withdrawing from the study due to unsatisfactory effectiveness of the assigned treatment, the Investigator will make attempts to improve therapy during a study visit. When a subject is withdrawn early from the study, a Study Termination eCRF will be completed describing the reason for discontinuation. Study staff will contact subjects to remind them about their scheduled visits and make sufficient efforts to locate a subject that is not responding to a contact call. In situations where study withdrawal is due to an adverse event, subjects will be followed until resolution of the adverse event or determination that the adverse event is not likely to change.

B.6.20. Study Completion

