B.7. Study Endpoints

B.7.1. Definition of Analysis Populations

- Modified Intent to Treat (mITT): All successfully randomized subjects who complete the Trial Phase.
- Intent-to-Treat (ITT): All successfully randomized subjects who met all the enrollment criteria.
- Per-Protocol (PP): All subjects who received a permanent device implant and contributed their data to the 3-month endpoint without any major protocol deviations or adverse events (that would render their data unevaluable).

The primary analysis of the primary and secondary endpoints will be performed on the mITT population. Supportive analyses will be performed for the Intent-to-Treat and Per-Protocol population.

For analyses incorporating crossover data (i.e. data gathered in the post 6-month periods), analyses will be based on the mITT population with treatment group defined by the treatment status at the corresponding time point to capture the impact of crossover. Additional sensitivity analyses censoring data post-crossover will be performed to examine the impact of crossover.

B.7.2. Effectiveness Assessment Definitions

- Primary Effectiveness Assessment: For subjects who have a successful Trial Phase and receive a permanent implant, the Primary Efficacy Assessment occurs at the follow up visit 3 months after Device Activation. For subjects who do not have a successful Trial Phase (based on subject's pain score) or subjects who do not want a permanent device implant due to insufficient pain relief (based on subject's discontinuation reason), the Primary Efficacy Assessment occurs at the end of the Trial Phase.

B.7.3. Primary Endpoint

Pain rating on the 10 cm Visual Analog Scale is considered the primary outcome measure. VAS is the most widely used outcome measure in assessing pain due to its documented reliability and validity, ease in administration, and minimal training requirements for the administrator.

- ***Individual Responder:*** A decrease in back pain VAS by at least 50% at 3 months after Permanent Device Activation as compared with Baseline. All subjects must be using the assigned programming parameters. If a subject is switched to a programming parameter that is not considered to be DTM-SCS nor Conventional SCS programming the subject will be counted as a non-responder for the following follow-up visit if one of the two following conditions exist:

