 - If a subject is switched to a programming parameter that is not considered to be DTM-SCS nor Conventional SCS programming for a period over two weeks
 - If a subject is switched to a programming parameter that is not considered to be DTM-SCS nor Conventional SCS programming for any length of time within the 2 weeks prior to a follow-up visit.

Overall Study Success: The percentage of Individual Responders in the test group is shown to be statistically non-inferior to the percentage in the control group.

B.7.4. Secondary Endpoints

The following secondary endpoints will be evaluated:

- Comparison of the percentage of Individual Responders between the test and control groups in a statistical test of superiority over time (i.e. based on repeated measures analysis). In addition, data will be summarized at the individual time points at 3 months, 6 months, 9 months, and 12 months. This will be performed based on all observed data with treatment defined as a time dependent covariate, and additionally based on censoring data post-crossover.

- Comparison of change from Baseline in back pain score (VAS) between test and control in statistical tests of non-inferiority and superiority. This is calculated as: Change from Baseline in Back Pain VAS = Follow-up Visit Pain VAS – Baseline Pain VAS. A negative result reflects a decrease in the Pain VAS, while a positive result reflects an increase in Pain VAS. All subjects must be using the assigned programming parameters. If a subject is switched to a programming parameter that is not considered to be DTM-SCS nor Conventional SCS programming, that subject's Baseline Back Pain VAS will be used instead of Follow-up Visit VAS after the programming change has occurred for the following follow-up visit if one of the two following conditions exist:
 - If a subject is switched to a programming parameter that is not considered to be DTM-SCS nor Conventional SCS programming for a period over two weeks
 - If a subject is switched to a programming parameter that is not considered to be DTM-SCS nor Conventional SCS programming for any length of time within the 2 weeks prior to a follow-up visit.

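### B.7.3 gives no month-3 scoring rule for a subject moved to the other arm's programming, and the only arm-specific penalty (B.4) falls on Control

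*Combined protocol and SAP*

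**What the plan says.** **Responder definition (B.7.3).** The definition asks for a back pain VAS reduction of at least 50% at 3 months and adds: "All subjects must be using the assigned programming parameters". It then says how a departure is scored, for a subject "switched to a programming parameter that is not considered to be DTM-SCS nor Conventional SCS programming the subject will be counted as a non-responder". Either of two conditions must also hold: the departure lasted more than two weeks, or it occurred "for any length of time within the 2 weeks prior to a follow-up visit".

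**VAS change (B.7.4).** The same requirement, trigger and conditions are repeated. The consequence is that "that subject's Baseline Back Pain VAS will be used instead of Follow-up Visit VAS after the programming change has occurred".

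**Treatment groups (B.4).** For Control: "If frequency parameter above 250 Hz is used during the study, the subject will be counted as failure towards Conventional SCS programming approach". For Test, the section describes the programming ("Each DTM-SCS program group has at least two programs with different pulse rate in the 50 to 1,000 Hz range") and attaches no failure rule.

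**Crossover (B.6.14).** "After the 6 month assessment is completed, subjects in both arms will have an option to change to the other arm". No section permits a change of arm before then.

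**Populations (B.7.1).** The primary analysis uses the mITT population. Per-Protocol, which excludes major deviations, is supportive. Grouping by current treatment is tied in B.7.1 to data gathered after 6 months.

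**The concern.** Before month 6, a subject can leave the assigned programming for something outside both approaches or for the other arm's approach. The plan gives a score and timing limits for the first and none for the second. The second matters more for the comparison, because the outcome obtained under one treatment would be credited to the other.

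In a non-inferiority trial the risk has a direction. If Test subjects doing poorly on DTM are moved to the comparator and any response is counted for DTM, the arms are pulled together and a real deficit is harder to see. Under B.8.2, non-inferiority on this endpoint is the only criterion for study success. The trial is also open-label (B.5.4), so a scoring choice left open could be settled by people who already know the assignments and the outcomes.

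**Working it through.** **1. Which departures before month 6 have a stated score?**

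| Departure | B.7.3 / B.7.4 trigger met? | B.4 failure rule met? |
|---|---|---|
| Either arm to programming that is neither approach | Yes, if a two-week condition holds | Control only, if above 250 Hz |
| Control to DTM, any rate above 250 Hz | No | Yes |
| Control to DTM, all rates at or below 250 Hz | No | No |
| Test to Conventional | No | No rule exists for Test |

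Two further mismatches follow. B.4 has no two-week tolerance, so a Control subject run briefly above 250 Hz on programming that is neither approach is a failure under B.4 but may escape B.7.3. B.4 also applies throughout the study, so on its face it reaches Control subjects who make a permitted crossover to DTM.

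**2. Can the two approaches be told apart?** Conventional is 40-250 Hz; DTM is two or more programs at different rates within 50-1,000 Hz. The ranges share 50-250 Hz, so rate alone does not classify a setting. The device log is optional in Table 1, and no section says that settings are captured on the eCRF.

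**3. The plan's own sample size.** Inputs from B.5.5.1: 70% v 50%, margin 10 points, one-sided alpha 0.05, 50 per arm, Farrington-Manning test.
- Restricted estimates under the null: 0.544 (Test) and 0.644 (Control).
- Null SE = √[(0.544×0.456 + 0.644×0.356)/50] = 0.0977.
- Alternative SE = √[(0.70×0.30 + 0.50×0.50)/50] = 0.0959.
- Power = Φ[(0.20 + 0.10 − 1.645×0.0977)/0.0959] = Φ(1.452) = 92.7%. Exact binomial enumeration also gives 92.7%.

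The stated 90% or greater is reproduced. The sample size is sound and is not the issue.

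**4. Illustration at the non-inferiority boundary.** One subject is 1/50 = 2 points. Take 40% as the true Test rate with switched subjects not credited, against 50% in Control. Add net credited Test responders and enumerate the exact Farrington-Manning rejection probability at 50 per arm:

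| Net credited Test subjects | Shift | Test rate | False non-inferiority |
|---|---|---|---|
| 0 | 0 | 40% | 4.7% |
| 1 | +2 points | 42% | 6.9% |
| 2 | +4 points | 44% | 9.9% |
| 4 | +8 points | 48% | 18.7% |

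The number of credited subjects is an assumption; the documents give no switching rate.

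**5. Cost of stricter scoring under the design assumptions.** Let a share s of Test subjects switch, with switchers responding at 50% and the others at 70% (all assumed).
- s = 5%: switchers scored non-responders, 0.70×0.95 = 66.5%, power 85.3%. Observed response kept, 66.5% + 0.50×5% = 69.0%, power 91.0%.
- s = 10%: 0.70×0.90 = 63.0%, power 74.6%. Observed response kept, 63.0% + 0.50×10% = 68.0%, power 88.9%.

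**The case against.** The strongest reply is that the requirement to use the assigned programming stands inside the responder definition, just before the scoring rule. On that reading a Test subject on Conventional does not meet the definition. A reader might infer from the scoring rule that the plan lets such a subject count for DTM without consequence; because of that sentence, the documents do not support so strong a claim.

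The requirement still does not settle the score. It has no timing, so it is unclear whether one day off assignment disqualifies or only status at the visit. If it already made every departure a non-response, the narrower rule would be redundant and its two-week tolerance would contradict it. For VAS change it names no substitute value.

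A reader might also infer that investigators are told to use the other arm's programming as rescue. They are not. For subjects considering withdrawal for poor effect, B.6.19 says "the Investigator will make attempts to improve therapy during a study visit" and does not mention the other arm. During the Trial Phase, a DTM subject with insufficient relief is directed to another DTM program group (B.4, B.6.6). Different companies' representatives program each arm (B.5.2). An early switch would be an unpermitted deviation, perhaps a rare one. It remains feasible: both approaches run on the same device (A.2), programming can be adjusted at activation, month 1 and unscheduled visits (B.6.9, B.6.10, B.6.12), and remote programming is allowed (B.9.1).

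There are partial safeguards. Per-Protocol may exclude such subjects, but it is supportive and does not define a major deviation. The repeated-measures secondary models use current treatment status (B.7.4, B.9.2.2), so there a switched subject need not be credited to DTM. The gap therefore concerns mainly the month-3 primary test and the month-3 tests in B.9.2.2.

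**Conclusion.** The point holds as a mis-scoped scoring rule. For visits before a permitted crossover, the plan states no score for a subject on the other arm's programming, and two competent analysts could score the same subject differently in the mITT primary analysis. The one explicit arm-specific penalty lowers only the Control rate, which favours the test arm. Nothing in the documents shows that this was intended.

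The size is unknown because it depends on how many switches occur. The boundary figures in the working show only that a few subjects matter at 50 per arm: two net credited subjects roughly double the false non-inferiority rate. This should be fixed before analysis. It does not undermine the design or the sample size.

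**What to change.** 1. In B.7.3 and B.7.4, for the month-3 primary endpoint, the month-3 VAS test and any other visit before a permitted crossover, change the trigger to *not the programming approach to which the subject was randomized*. Keep the same two-week conditions in both arms. Keep the present trigger for visits after a permitted crossover.
2. Reconcile this analysis rule with B.4: whether failure there means non-response on the primary endpoint, whether the two-week conditions apply, and how it treats permitted crossover.
3. Define, for analysis purposes, how DTM and Conventional are distinguished where their rate ranges overlap, and confirm that settings and dates from programming visits are recorded so the rule can be applied.
4. Add a sensitivity analysis of the primary endpoint that keeps switched subjects' observed response. This is needed because scoring switched Control subjects as non-responders lowers the Control rate and so itself favours non-inferiority.

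The cost is a few sentences in the protocol or SAP, one extra analysis and, if settings are not already captured, a small data-collection addition. No further subjects are needed. If switches occur, responder rates will be slightly lower and some power will be lost.

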Analysis of both secondary endpoints will be based on a repeated measures approach that accounts for within subject correlation. Treatment group status for the repeated measures models will be based on treatment status at the current time point (i.e. it will be based on treatment status incorporating potential crossover, not necessarily the original randomized assignment).

B.7.5. Additional Data Collection

These following data will be collected:

- Frequency of treatment emergent adverse events
- Comparison of opioid medication usage from baseline at 3, 6, 9 and 12 months after device activation between the two arms
- Comparison of mean change from Baseline in Leg Pain VAS, evaluated at 3, 6, 9 and 12 months after device activation for subjects with baseline leg pain VAS score ≥ 5 between test and control
- Comparison of Leg Pain Treatment Success, measured as at least a 50% reduction in Leg Pain VAS, evaluated at 3, 6, 9, and 12 months after device activation for subjects with baseline leg pain VAS score ≥ 5 between test and control
- Comparison of patient satisfaction between two arms
- Patient Global Impression of Change, evaluated at 3, 6, 9 and 12 months after device activation
- Comparison of Patient Global Impression of Change between two arms

- Comparison of ODI change from baseline at 3, 6, 9 and 12 months after device activation between the two arms
- Comparison of quality of life (QoL) change (from EuroQol EQ-5D-5L) from baseline at 3, 6, 9 and 12 months after device activation between the two arms
- Quality of paresthesia at 3, 6, 9 and 12 months, comparison between test and control
- Percentage of subjects that crossover
- Comparison of mean change from last visit prior to crossover to 12 months visit. This analysis censors data post-crossover.
- Activity level based on Intellis™ adaptive data log (when available)
- Analysis of additional evaluable data items will be based on treatment status at the current time point (i.e. it will be based on treatment status incorporating potential crossover, not necessarily the original randomized assignment).

B.8. Evaluation Criteria

B.8.1. Effectiveness

Results of the tests and standard questionnaires will be recorded in Case Report Forms at Baseline and during follow-up visits. Changes from Baseline will be calculated and compared between the two groups.

Effectiveness will be measured for each subject using the following tests:

- Pain

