A 10% margin has been previously used in a similar study.¹⁶ Meeting the statistical threshold for this test based on a 10% margin should produce clinically acceptable results.

B.9.2.2 Secondary Analyses

The following *secondary endpoints* will be evaluated:

- If the primary efficacy endpoint in the test group is found to be non-inferior to that in the control group, then a secondary endpoint will evaluate whether the proportion of subjects who achieve a 50% improvement in their back pain VAS score at 3 months in the test group is superior to that in the control group. A superiority test based on the difference in proportions will be performed based on the following null hypothesis, with a one-sided p-value of 0.05 or less considered evidence of statistical significance.

H_0 : The proportion of subjects (P) who achieve a 50% improvement in their back pain VAS score at 3 months in the Test group is less than or equal to that in the Control group.

$$P_{\text{Test}} \leq P_{\text{Control}}$$

H_1 : The proportion of subjects (P) who achieve a 50% improvement in their back pain VAS score at 3 months in the Test group is greater than that in the Control group.

$$P_{\text{Test}} > P_{\text{Control}}$$

- Change in mean VAS will be evaluated with two-sample t-test of non-inferiority in means with a 0.65 cm margin at 3 months.

H_0 : The change (C) in subject's VAS pain intensity score relative to baseline at the Primary Efficacy Assessment in the Test group is inferior to that of subjects in the Control group (active control).

$$C_{\text{Test}} \geq C_{\text{Control}} - 0.65 \text{ cm}$$

H_1 : The change (C) in subject's VAS pain intensity score relative to baseline at the Primary Efficacy Assessment in the Test group is not inferior to that of subjects in the Control group (active control).

$$C_{\text{Test}} < C_{\text{Control}} - 0.65 \text{ cm}$$

The non-inferiority margin of 0.65 cm was selected based on a previous study of a similar therapy against traditional SCS¹⁶. In that study, the experimental therapy showed a 4.9 point improvement while traditional SCS showed a 3.6 point improvement for a difference of 1.3 points. Taking 50% of this treatment effect yields the margin of 0.65.

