The following secondary endpoints do not have an associated hypothesis, and no significance level will be assigned to statistical tests that may be performed. Analysis of these endpoints will be based on a repeated measures approach that accounts for within subject correlation. Treatment group status for the repeated measures models will be based on treatment status at the current time point (i.e. it will be based on treatment status incorporating potential crossover, not necessarily the original randomized assignment).

- Comparison of Back Pain Treatment Success (responder rate), measured as subjects with at least a 50% reduction in Back Pain VAS, between test and control
- Comparison of mean change from Baseline in Back Pain VAS, between test and control

B.9.2.3 Additional Data

- Comparison of Leg Pain Treatment Success (responder rate), measured as subjects with at least a 50% reduction in Leg Pain VAS, between test and control for subjects with baseline leg pain VAS score ≥ 5
- Comparison of mean change from Baseline in Leg Pain VAS, between test and control for subjects with baseline leg pain VAS score ≥ 5
- *Satisfaction with Therapy*: Subject Satisfaction will be compared between test and control
- *Patient Global Impression Change*: The Patient Global Impression of Change from Baseline to follow-ups at 3-, 6-, 9- and 12-month visits after device activation will be compared between the treatment groups.

- *Oswestry Disability Index (ODI)*: The changes in ODI from Baseline to 3-, 6-, 9- and 12-months will be summarized as continuous variables and compared between the treatment groups.
- *Quality of Life*: The changes in the EQ-5D-5L instrument from Baseline to follow-ups at 3-, 6-, 9- and 12-months will be summarized as continuous variables and compared between the treatment groups.
- *Paresthesia Questionnaire*: Questions about the paresthesia will be used at 3-, 6-, 9-and 12-month visits and compared between test and control

B.9.2.4 Handling of Missing Data

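### B.7.4 and B.9.2.2 contradict each other on how the secondary endpoints are tested, so the plan does not fix which analysis supports a superiority claim

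*Combined protocol and SAP*

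**What the plan says.** **B.7.4 (Secondary Endpoints)** lists two endpoints.

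- Responders are compared between arms "in a statistical test of superiority over time (i.e. based on repeated measures analysis"). On the data used, it says: "This will be performed based on all observed data with treatment defined as a time dependent covariate, and additionally based on censoring data post-crossover".
- For back pain the entry reads "Comparison of change from Baseline in back pain score (VAS) between test and control in statistical tests of non-inferiority and superiority". It gives no margin, alpha or time point.

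The section closes with "Analysis of both secondary endpoints will be based on a repeated measures approach that accounts for within subject correlation" and takes treatment group as the status at each time point, after any crossover. It states no alpha, sidedness or dependence on the primary result.

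**B.9.2.2 (Secondary Analyses)** is different.

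- The responder test is conditional: "If the primary efficacy endpoint in the test group is found to be non-inferior to that in the control group", superiority is examined at 3 months. The method reads: "A superiority test based on the difference in proportions will be performed based on the following null hypothesis". The threshold for declaring a result is set out separately: "with a one-sided p-value of 0.05 or less considered evidence of statistical significance".
- VAS change gets a two-sample t-test of non-inferiority at 3 months with a 0.65 cm margin. No alpha is stated and there is no superiority hypothesis.
- Before listing the repeated-measures comparisons of responder rate and mean back pain change, it says: "The following secondary endpoints do not have an associated hypothesis, and no significance level will be assigned to statistical tests that may be performed".

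**B.8.2** rests study success on the primary non-inferiority test and sets no success criteria for secondary endpoints.

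**The concern.** The same two endpoints are given different time points, methods, treatment definitions and inferential status. One section calls the repeated-measures responder analysis a superiority test, and the other says it has no hypothesis. These are two stated rules in conflict, not a missing detail.

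The two responder analyses also estimate different quantities. The 3-month comparison precedes any crossover and compares the arms as randomised. The repeated-measures analysis pools later visits by current treatment. B.6.1 and B.6.14 offer crossover to subjects without sufficient relief, so treatment status at 9 and 12 months depends on earlier outcome. The two analyses can therefore disagree.

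Superiority is a claim the sponsor is likely to want. B.1 reports that an earlier randomised study of the same programming met superiority as a secondary objective. If the two results differ here, the plan leaves room to decide after seeing the data which one is the superiority test.

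**Working it through.** **1. The two sections side by side**

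| Item | B.7.4 | B.9.2.2 |
|---|---|---|
| Responder superiority: method | Repeated measures over time | Difference in proportions at 3 months |
| Treatment definition | Current status, and again with post-crossover data censored | 3-month comparison, before crossover opens |
| Alpha and condition | None stated | One-sided 0.05, only after primary non-inferiority |
| VAS non-inferiority | Repeated measures; no margin or alpha | 3-month t-test, 0.65 cm; no alpha |
| VAS superiority | Listed, not specified | Absent |
| Status of repeated measures | The stated method for both endpoints | No hypothesis, no significance level |

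Only VAS non-inferiority is defined twice. VAS superiority is named once and never specified.

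**2. The plan's own sample size (B.5.5.1)**

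Inputs: 70% against 50%, margin 10 points, one-sided alpha 0.05, 50 per arm. Under the Farrington-Manning null the restricted estimates are 0.544 (test) and 0.644 (control).

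- Null SE = sqrt((0.544×0.456 + 0.644×0.356)/50) = 0.0977
- Alternative SE = sqrt((0.7×0.3 + 0.5×0.5)/50) = 0.0959
- Power = Φ((0.20 + 0.10 − 1.645×0.0977)/0.0959) = Φ(1.452) = 92.7%

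The stated power of about 90% or more is reproduced. No power is given for any secondary test.

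**3. Power of the 3-month superiority test on the same inputs**

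- Pooled null SE = sqrt(2×0.6×0.4/50) = 0.0980
- Power = Φ((0.20 − 1.645×0.0980)/0.0959) = Φ(0.405) = 65.7%

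At 50 per arm the formal superiority test would miss about one time in three even if the planning rates were true. About 74 per arm would give 80%. So the ambiguity could well matter in practice.

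**4. Error if either responder test could carry the claim**

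Assumptions not in the documents: one-sided 5% for both tests, four complete visits (3, 6, 9 and 12 months), compound symmetry with within-subject correlation ρ, no effect and no crossover. The correlation between the 3-month statistic and the four-visit average is r = sqrt((1+3ρ)/4). The chance that at least one exceeds 1.645 is 1 − Φ2(1.645, 1.645; r).

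| ρ | r | At least one significant |
|---|---|---|
| 0.2 | 0.632 | 8.3% |
| 0.3 | 0.689 | 8.1% |
| 0.5 | 0.791 | 7.6% |
| 0.7 | 0.880 | 7.0% |
| 0.8 | 0.922 | 6.6% |
| 0.9 | 0.962 | 6.1% |

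For reference, two independent tests would give 1 − 0.95² = 9.75%. Holding 5% over both tests would need about 0.029 (ρ = 0.2) to 0.041 (ρ = 0.9) per test.

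A simulation under no effect (50 per arm, assumed underlying correlation 0.5 or 0.8, assumed crossover of 0 to 50% among 6-month non-responders) gave 6.4% to 9.7% for the 3-month test or the as-treated analysis. Adding the crossover-censored version as a third route gave 6.4% to 11.1%. With 4,000 runs per setting, the standard error sqrt(p(1−p)/4000) is 0.4 to 0.5 points.

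**5. The printed VAS hypothesis**

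B.7.4 defines change as follow-up minus baseline, so a negative value is improvement. B.9.2.2 prints H1 as C_Test < C_Control − 0.65 cm. Take equal arms, each improving by 3.6 (the traditional SCS figure in B.9.2.2). H1 then requires −3.6 < −4.25, which is false. As printed, the test arm must be better by more than 0.65 cm, which is stricter than superiority. With the sign reversed, the condition is −3.6 < −2.95, which holds, as a non-inferiority alternative should.

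**The case against.** The best defence is that B.9.2.2 is the analysis section and the more specific text. It alone gives the responder superiority test a null hypothesis, an alpha, a time point and a condition, and it expressly withholds a hypothesis from the repeated-measures comparisons. On that reading B.7.4 is loosely worded and only one formal superiority claim exists. This has force: read alone, B.9.2.2 allows a formal claim only from the gated 3-month test. But nothing says that B.9.2.2 prevails. B.7.4 is the section that defines the endpoints, and its closing sentence covers both of them. The separate statistical analysis plan is mentioned in B.9.2.4 for imputation details only.

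Three further objections stand in part.

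- The error figures give the repeated-measures test a 5% level that the plan never assigns. They are conditional and are presented as such.
- B.6.7 carries data from unimplanted Trial Phase failures forward to the secondary endpoints. Read literally, this repeats one value across visits, raises the correlation and moves the figure towards the lower end of the range.
- Crossover opens only after the 6-month assessment, and a version censoring later data is pre-specified. Distortion from crossover is therefore confined to the 9- and 12-month data of the as-treated analysis.

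**Conclusion.** The plan is wrong as written on this point: B.7.4 and B.9.2.2 give incompatible rules for the secondary endpoints. The consequence is limited. Primary study success does not depend on it, and the excess error is modest: about 6.1% to 8.3% against 5%, if both responder tests were read at one-sided 5% and the within-subject correlation lies between 0.9 and 0.2. Both conditions are assumptions.

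A reader might infer that the plan permits superiority to be claimed from either analysis. It contains no such rule; the freedom comes only from the unresolved conflict. A reader might also infer that all the VAS tests are defined twice, which is true of non-inferiority only, or that the trial's overall type I error is inflated, which B.8.2 rules out for the declared success criterion.

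**What to change.** **Responders.** In B.7.4, replace the wording "in a statistical test of superiority over time (i.e. based on repeated measures analysis") and the sentence "Analysis of both secondary endpoints will be based on a repeated measures approach that accounts for within subject correlation". Name the 3-month, as-randomised mITT difference in proportions, tested only after primary non-inferiority, as the sole responder superiority test. Label every repeated-measures result, as-treated and crossover-censored, as descriptive. B.9.2.2 already treats them so.

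**VAS.** Name the 3-month comparison as the only VAS hypothesis test. First correct the sign of the margin in B.9.2.2:

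- H0: C_Test ≥ C_Control + 0.65 cm
- H1: C_Test < C_Control + 0.65 cm

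State its alpha, one-sided 0.05 to match the other tests. Then either place VAS superiority after VAS non-inferiority in a fixed order with its own hypothesis, or delete it. Write the order out, because B.9.2.2 at present makes only the responder test conditional on the primary.

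**Cost.** The change is protocol wording only, with no added visits, data or subjects. The repeated-measures superiority test loses any confirmatory status. The corrected VAS test is easier to pass than the printed one, so the change should be documented before any comparison between arms is run.
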